### 2) IRB Review History

The HRRC reviewed this study on 2/10/2015, and after requested modifications were completed, the HRRC approved it on 4/17/2015. A modification to add research assistants was reviewed and approved by the HRRC on 5/19/2015. Post-approval monitoring was conducted by the HRPO on 10/21/2015.

### 3) Objectives

We hypothesize that apneic oxygenation via nasal cannula during airway placement improves oxygen saturation in pediatric patients. Patients who receive this treatment will be compared to patients managed under the current standard of care, which does not include apneic oxygenation during anesthetic induction and airway management.

The primary outcome is the elapsed time between anesthetic induction and pulse oximetry (SPO2) falling to 95%, if it happens at all.

The secondary outcomes are as follows:

- whether the 95% threshold is met at all
- whether intervention by attending or temporary mask ventilation is required
- whether pulse oximetry falls to 90%
- the lowest observed pulse oximetry during airway placement

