### 4) Background

This observational study aims to investigate the effect of a planned practice change; instituting oxygenation via nasal cannula during induction of anesthesia. The use of a nasal cannula during the peri-intubation period is of minimal risk and is not considered a standard of care in pediatric anesthesia. Some providers use it in certain clinical situations, but it is not broadly used and has virtually no pediatric literature to support or refute its use.

At our institution, intubation of pediatric patients by inexperienced (learner) providers under expert supervision is routine. The attending

physician intervenes if necessary before the patient experiences excessive loss of oxygenation.

There has been increasing discussion of nasal cannula apneic oxygenation in the adult anesthesia and emergency medicine literature, but there is a paucity of pediatric literature to support or refute its use in the pediatric population. Weingart and Levitan 2012, discuss how Apneic oxygenation is based on the physiology of the lungs absorbing a greater volume of oxygen, 250 ml/min in an adult, than the volume of carbon dioxide, 8-20 mL/min, that is released by the lungs as the majority of carbon dioxide is buffered in the blood stream during apnea. With the imbalanced volumes of absorption and release of gasses in the lungs there is a lower than atmospheric pressure in the lungs, creating a passive movement of gases from pharynx to alveoli. If the gas in the pharynx has a significantly higher percentage of oxygen instead of room air at 21% oxygen, a higher amount of oxygen can be passively delivered to the lungs for absorption prolonging the time to hemoglobin desaturation.

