## 11) Study Methods

This is a prospective observational study. Prospectively-recorded data are necessary because data on the outcomes of interest are not available in the medical record.

Participants will be enrolled in the study once they have entered the pre-operative area and they are determined by the attending anesthesiologist to

that they are an eligible study participant. Participants enrolled in the first three months of the study will be assigned to the baseline condition as described below. Participants enrolled in the second phase of the study will be assigned to the with-cannula condition described below.

A patient sticker will be added to the data collection form. Basic demographic information and vitals will be recorded before premedication is administered as is standard at entry to the pre-operative area. Timing devices of the same make and model will be used consistently between all study cases.

For the **baseline group** of this observational study, all intubation procedures will be performed as per usual practice. Patients will receive premedication as determined by anesthesiologist/resident/midlevel, and the type and dose will be recorded.

Once patients are brought to the operating room suite and vital signs are being monitored, patients will be preoxygenated via mask per standard of care, with an expired oxygenation concentration minimum of 0.75. Vitals will be recorded at the moment prior to removal of the face mask at the end of the preoxygenation period. Anesthetic induction will then be performed with agents and dosages as per the provider's clinical judgment.

Airway management consisting of oral endotracheal intubation or laryngeal mask airway insertion will take place. As per usual practice, an attending physician who is expert in pediatric airway management will supervise the procedure and intervene before the patient experiences excessive oxygen desaturation. The lowest oxygen saturation and the time to either successful intubation or intervention by an attending physician will be recorded.

For the **with-cannula group**, all of the above steps will be maintained. The sole difference will be nasal cannula placement after induction. It will be set to deliver 5L of oxygen per minute.

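### Does leaving the exact start of the induction clock unstated undermine the primary comparison of two groups enrolled in sequence?

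*Combined protocol and SAP*

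**What the plan says.** Section 3 starts the primary clock at induction: "The primary outcome is the elapsed time between anesthetic induction and pulse oximetry" falling to 95%. Section 14 analyses it by Kaplan-Meier and survival methods, censoring at successful intubation or attending intervention. Section 6 bases the sample size on a one-tailed logrank test.

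Section 11 gives the sequence of steps. At the end of mask preoxygenation, "Vitals will be recorded at the moment prior to removal of the face mask at the end of the preoxygenation period". Next, "Anesthetic induction will then be performed with agents and dosages" left to the provider. In the with-cannula group, "The sole difference will be nasal cannula placement after induction". On timing it says only this: "Timing devices of the same make and model will be used consistently between all study cases". It also records the time to intubation or attending intervention, without giving that time an origin.

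Allocation is by calendar period: "Participants enrolled in the first three months of the study will be assigned to the baseline condition", and the second phase receives the cannula. Section 4 words the practice change differently, as "instituting oxygenation via nasal cannula during induction of anesthesia". Section 3 describes the comparator as current care, "which does not include apneic oxygenation during anesthetic induction and airway management". Section 12 lists a data collection form, which is not part of the supplied text.

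**The concern.** Induction is a process of variable length, not an instant. The timer could be started at mask removal, at the first agent, at loss of consciousness or at the end of induction, and the text names none of these. Under random allocation, variation in that habit would fall roughly equally on both groups. Here the groups are separated in time, so a drift in habit is fully confounded with treatment. The with-cannula phase also adds a step near time zero. On section 11's wording, that step lies inside the timed interval.

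At stake is the validity of the primary test. If the timer tended to start earlier relative to apnea in the second phase, every with-cannula case would carry extra event-free seconds and the logrank test would favor the cannula spuriously. If it tended to start later, a real effect could be missed.

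**Working it through.** **The plan's own figure.** With a hazard ratio of 0.5, one-sided 5% and 80% power, Freedman's formula gives (1.645 + 0.842)² × (1.5/0.5)² = 55.64 events. Dividing by 0.15 gives 370.95, the 371 patients of section 6. It uses event proportions only; no clock definition enters it. (It applies 15% to both groups. That is a separate matter.)

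**Inputs for the check.** From section 6: 200 + 200 patients, 15% reaching 95%, halved to 7.5%, one-sided 0.05. Hence HR = ln(0.925)/ln(0.85) = 0.48, and expected events are 400 × 0.1125 = 45. Power by Freedman is Φ(√45 × 0.52/1.48 − 1.645) = Φ(0.71) ≈ 76%, close to the 77% simulated with no shift.

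Assumed, because the documents give no durations: median airway time 30, 60 or 120 s (lognormal, log SD 0.5), and a systematic group difference of 5, 10 or 15 s. Desaturation risk is constant, or rising (Weibull shape 3). Each cell has 10,000 simulated trials.

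**1. Same start moment in both groups, apnea from induction, cannula placement adding 5 to 15 s.** Null rejection is 4.7% to 5.8% for every median and both risk shapes. At a 60 s median the with-cannula share reaching 95% would go from 15% to 16%, 17% or 18%. That is a consequence of the practice being studied and not a bias in the test.

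**2. Timer start shifted in every with-cannula case, constant risk.**

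| Median airway time | Null rejection, start 5 / 10 / 15 s earlier | Power, start 5 / 10 / 15 s later |
|---|---|---|
| 30 s | 16% / 35% / 61% | 58% / 35% / 15% |
| 60 s | 9% / 16% / 25% | 68% / 58% / 47% |
| 120 s | 7% / 9% / 12% | 73% / 68% / 64% |

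With rising risk, null rejection is 36% / 83% / 98% at 30 s, 17% / 37% / 62% at 60 s and 9% / 16% / 25% at 120 s. The 61% and 98% cells need a shift of 15/30, half the assumed median airway time, in every case of one phase.

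**3. Placement adds seconds without desaturation risk** (mean induction-to-apnea gap 60 s, SD 20 s, constant risk). Null rejection at 60 s is 9% / 15% / 22%. This needs placement time to be risk-free, although section 11 takes the mask off before induction and puts the cannula on after it.

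**4. The timer-free outcome.** Whether SpO2 reaches 95% is a yes/no fact for each child. Adding or subtracting a constant from the recorded times leaves it unchanged. Under the shifts in step 2 the two-proportion test rejects a true null 4.5% to 5.4% of the time in every cell. With a true halving it keeps about 76% power one-sided (66% two-sided; section 14 does not state the side) whatever the shift.

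**5. Whether extra time stamps would settle it.** The 95% half-width for a group difference in induction-to-first-attempt time is 1.96 × SD × √(1/200 + 1/200): 3.9 s for SD 20 s and 7.8 s for SD 40 s (SDs assumed). With 100 usable baseline cases it is 4.8 s or 9.6 s. A longer interval could mean an earlier timer start or longer apnea, and the comparison cannot separate them. An analysis timed from the first attempt holds 4.6% to 5.3% if the extra seconds are event-free, but falls to 2.8% / 1.4% / 0.8% (60 s median) if they are apneic.

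**The case for a change.** The strongest case for acting is that a time-to-event primary outcome needs a common time zero, that nothing in a before-after design balances a drift in it, and that shifts of 5 to 10 s are enough to matter when airway times are short. Naming the start event would cost almost nothing. The timer-free outcome is also only a coarse safeguard: with 15% in each group, the 95% half-width for the difference is 1.96 × √(2 × 0.15 × 0.85/200) = 7.0 percentage points, against a planned difference of 7.5. It can flag a discordant logrank result but cannot repair the primary p-value.

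The arithmetic stands, and so does the observation that the supplied text gives no start event. What does not stand is the step from an unwritten definition to a flawed comparison. The direction and size of any drift are assumed throughout. Nor is it right that the analysis would be blind to a shift: besides reaching 95%, the planned secondary outcomes of reaching 90%, lowest SpO2 and need for intervention use no timer.

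The differing wording on cannula timing adds little. Section 4 is background, and section 3's hypothesis places the oxygen in the airway placement period. The wordings in sections 4 and 11 should be reconciled as a clerical matter; no view is taken here on which order is right.

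**Conclusion.** The gap is real but is one of documentation, and the data collection form may already close it. The sensible reading is one start event, the same for every child, serving both event and censoring times and carried over unchanged from the baseline cases that section 6 shows were already being enrolled. Read that way, the logrank test holds its level (4.7% to 5.8%) and the cannula step inside the interval is part of the practice under study.

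Inflation to 7% to 61% under constant risk (up to 98% under rising risk) requires a systematic shift of 5 to 15 s between phases, with airway times that the documents do not give. The planned share reaching 95% is untouched by such a shift and can be read beside the primary result. Further time stamps or a first-attempt analysis would leave the primary result as it is, could not separate early timing from longer apnea, and might be impossible for baseline cases already enrolled. No change to the plan follows. The conclusion would differ only if there were evidence that the start was marked differently in the two phases, and the documents contain none.

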### 4) Background

This observational study aims to investigate the effect of a planned practice change; instituting oxygenation via nasal cannula during induction of anesthesia. The use of a nasal cannula during the peri-intubation period is of minimal risk and is not considered a standard of care in pediatric anesthesia. Some providers use it in certain clinical situations, but it is not broadly used and has virtually no pediatric literature to support or refute its use.

At our institution, intubation of pediatric patients by inexperienced (learner) providers under expert supervision is routine. The attending

physician intervenes if necessary before the patient experiences excessive loss of oxygenation.

There has been increasing discussion of nasal cannula apneic oxygenation in the adult anesthesia and emergency medicine literature, but there is a paucity of pediatric literature to support or refute its use in the pediatric population. Weingart and Levitan 2012, discuss how Apneic oxygenation is based on the physiology of the lungs absorbing a greater volume of oxygen, 250 ml/min in an adult, than the volume of carbon dioxide, 8-20 mL/min, that is released by the lungs as the majority of carbon dioxide is buffered in the blood stream during apnea. With the imbalanced volumes of absorption and release of gasses in the lungs there is a lower than atmospheric pressure in the lungs, creating a passive movement of gases from pharynx to alveoli. If the gas in the pharynx has a significantly higher percentage of oxygen instead of room air at 21% oxygen, a higher amount of oxygen can be passively delivered to the lungs for absorption prolonging the time to hemoglobin desaturation.

Taha et al 2006, concluded the use of nasal cannula insufflation after preoxygenation can delay the onset of hemoglobin desaturation for a prolonged period of time during the subsequent apneic period in adults. Ramachandran et al 2009, demonstrated the ability to prolong oxygen saturations >95% and increase the lowest saturation level with use of a nasal cannula at 5 L/min during simulated difficult intubations in adult obese males. Weingart and Levitan 2012, recommend that nasal cannula apneic oxygenation can extend the safe apnea period after the use of sedatives and muscle relaxants in adults. With a variety of search terms only three relevant articles were found in pediatric anesthesia literature. Bhagwan 2013, in Pediatric Anesthesia, commented about Levitan's NoDesat article in EPmonthly 2012, endorsing how her use of the nasal cannula adjunct in the peri-intubation period has led to fewer desaturations and bradycardic episodes in infant intubations by resident physicians. Her opinions were based on her experiences, but no data was gathered or presented to support the claims in a form representing a true study. T.M. Cook 1998, wrote a paper discussing blood gas results during pediatric apneic oxygenation in intubated pediatric patients undergoing undergoing cardiac catheterization. The findings demonstrated that apneic oxygenation was likely safe for up to 10 minutes before hypoxia would occur. An earlier study by Kernisan et al 1987, also studied apneic oxygenation in pediatric patients. Patients were intubated and not ventilated and they found desaturation via pulse oximetry did not occur in patients at 3 minutes.

Physiologically, children have a higher oxygen consumption than adults, 5-10 mL/kg/min, compared to adults, 3mL/kg/min. This high metabolic rate leaves pediatric patients at higher risk for hemoglobin desaturation in the peri-intubation period. In a Hospital setting there can be prolonged time periods as airway devices are placed in certain patients. The current

adult literature indicates that peri-intubation nasal cannula oxygenation can decrease the occurrence of hemoglobin desaturation during prolonged intubations. There is some pediatric literature supporting the physiologic safety of apneic oxygenation for a brief period of time after endotracheal intubation. Our adaptation of using a nasal cannula in the peri-intubation period would be new to the pediatric literature and would hopefully further elucidate the potential effects during the peri-intubation period and investigate whether this benefit also extends to pediatric patients. There are anatomical differences in the pediatric airway compared to adults which may make the use of nasal cannula apneic oxygenation less beneficial in the pediatric population.

This minimal risk study would add to the literature extending this concept to the pediatric patient population. If the same results were to be found as in the adult patient population there is the potential for an improved less stressful pediatric intubation learning environment and improved patient care with fewer and less severe desaturations during the peri-intubation period.

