**14) Data Management**

Only study investigators will have access to study data. Study participants will be assigned a study number, and this number will be used in all data analyses. The data will be entered into an electronic database that will be stored on UNMHSC password-protected servers. The electronic data will only have study participant numbers and no identifiers that could link specific patients to the data. All data forms that bear identifiers will be securely destroyed (shredded) upon application to HRRC for study closure, so that only deidentified data remain when that application is made.

As noted above, data to be gathered include basic demographic data, data about the anesthetic induction procedure, and data about the patient's O2 saturation.

Routine demographic data will be analyzed with t-tests and Wilcoxon rank-sum tests, as appropriate depending on normality of data distributions. Categorical data will be analyzed with appropriate analyses, such as chi-square, Fisher's exact, risk ratio, and/or odds ratio.

The primary outcome of time to cross the 95% saturation threshold will be analyzed with Kaplan-Meier curves and survival analysis with "censoring" for cases in which the threshold was not crossed because of either successful intubation or intervention by the attending physician.

Secondary outcomes with continuous data (e.g. the lowest observed O2 saturation) will be analyzed with standard t-tests or Wilcoxon rank-sum tests, as appropriate depending on normality of data distributions. Secondary outcomes with binary data (e.g. whether intervention by the attending physician is required) will be analyzed with chi-square or Fisher's Exact tests as appropriate depending on cell counts.

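### First-operator experience is not named in the protocol text and enters no analysis, so a change in operator mix between the two calendar phases would bias the binary secondary outcomes and, under further conditions, the primary

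*Combined protocol and SAP*

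**What the plan says.** **Allocation.** Section 11 forms the groups by calendar time: "Participants enrolled in the first three months of the study will be assigned to the baseline condition as described below", and "Participants enrolled in the second phase of the study will be assigned to the with-cannula condition described below". There is no randomisation and no concurrent control. Section 6 expects enrolment to take about a year.

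**Operators.** Section 4 states that "intubation of pediatric patients by inexperienced (learner) providers under expert supervision is routine", with the attending stepping in when needed.

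**Recorded data.** Section 14 gives categories only: "data to be gathered include basic demographic data, data about the anesthetic induction procedure", and oxygen saturation data. For the airway itself, section 11 says: "The lowest oxygen saturation and the time to either successful intubation or intervention by an attending physician will be recorded". Provider type appears once, in connection with "premedication as determined by anesthesiologist/resident/midlevel, and the type and dose will be recorded". Section 12 lists a data collection form as an appendix; its contents are not in the text available for this review.

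**Analysis.** In section 14 the primary outcome is analysed by Kaplan-Meier curves and survival methods, censored at successful intubation or attending intervention. Section 6 powers it on a one-tailed log-rank test. The secondary outcomes get t-tests or Wilcoxon tests if continuous and chi-square or Fisher's exact tests if binary. No covariate, stratum or calendar-time term is named.

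**Secondary outcomes.** Section 3 includes whether 95% is reached at all, whether 90% is reached, and "whether intervention by attending or temporary mask ventilation is required".

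**The concern.** With consecutive phases, anything that changes over the enrolment year is aligned with treatment. Operator experience is a natural candidate. The protocol says learners do much of this work, and section 4 links desaturation to prolonged intubations. If learners make up a smaller share of first operators in the second phase, attempts are shorter and fewer children reach 95%, even if the cannula does nothing. A shift the other way would hide a real effect.

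The binary secondary outcomes are the most exposed, because a simple proportion takes no account of how long each child was at risk. They also carry weight: section 9 lets the study avoid an ineffectiveness finding at the interim if any outcome, primary or secondary, shows one-tailed p < 0.20.

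The outcome that counts attending intervention has an extra sensitivity. If an attending makes the first attempt, takeover by the attending has no obvious meaning, so that component would depend on how many cases start that way.

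**Working it through.** **1. Plan's own figure.** Inputs from section 6: baseline rate 15%, rate halved, one-tailed α = 0.05, 80% power. Freedman's formula with hazard ratio 0.5 gives events = (1.645 + 0.842)² × [(1 + 0.5)/(1 − 0.5)]² = 6.1826 × 9 = 55.64. Dividing by 0.15 gives 370.95, so the stated 371 reproduces when the baseline rate is applied to all patients. The point below does not depend on that figure. It uses only the 15%, the 200 per group and the one-tailed 0.05.

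**2. Binary secondary outcome (95% reached at all), no cannula effect.** The documents give neither operator mix nor risk by operator, so both are assumed: junior share 50% in phase 1 and 25–30% in phase 2; junior/experienced risks 20%/10% or 22.5%/7.5%. Both pairs average to the planned 15% at a 50% share: 0.5 × 0.20 + 0.5 × 0.10 = 0.15, and 0.5 × 0.225 + 0.5 × 0.075 = 0.15.

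Phase 2 rate: p₂ = s × (junior risk) + (1 − s) × (experienced risk), with s the junior share. Chance of a false claim = Φ[(0.15 − p₂)/SE − 1.645], with SE = √{[0.15 × 0.85 + p₂(1 − p₂)]/200}.

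Example, 20%/10% and s = 0.25: p₂ = 0.05 + 0.075 = 0.125; SE = √[(0.1275 + 0.1094)/200] = 0.0344; 0.025/0.0344 = 0.726; Φ(0.726 − 1.645) = 0.18.

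| Risks (junior/experienced) | Junior share in phase 2 | p₂ | Apparent risk ratio | False benefit |
|---|---|---|---|---|
| 20% / 10% | 30% | 13.0% | 0.87 | 14% |
| 20% / 10% | 25% | 12.5% | 0.83 | 18% |
| 22.5% / 7.5% | 30% | 12.0% | 0.80 | 22% |
| 22.5% / 7.5% | 25% | 11.25% | 0.75 | 30% |

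With no change in share the rate stays at 5%.

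**3. Same outcome, opposite shift, cannula truly halves risk.** Junior share 50% to 70% with 20%/10%: p₂ = (0.14 + 0.03)/2 = 8.5%, power 65%. Share 50% to 75% with 22.5%/7.5%: p₂ = (0.16875 + 0.01875)/2 = 9.375%, power 53%. With no shift (15% against 7.5%), power is 77%.

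**4. Primary outcome (log-rank).** The scenarios of step 2 were simulated with Weibull desaturation times (shape 1 to 3) and independent lognormal attempt times.

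- *Operators differ only in attempt length.* One-sided rejection was 4.4–5.4%, against 15–30% for the two-proportion test on the same data. A quicker operator's patients are censored earlier, and the log-rank test compares only children still at risk at the same elapsed time.
- *Operators also differ in hazard at equal elapsed time.* Log-rank rejection rose to about 15–33%.

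A separate approximation with other assumed inputs gives a similar picture when learners carry a higher hazard. Let the learner share fall from 70% to 50% with learner risk twice that of others. The experienced rate is 0.15/(0.3 + 0.7 × 2) = 8.82%, and the phase 2 rate is 8.82% × (0.5 + 0.5 × 2) = 13.2%. The spurious hazard ratio is ln(1 − 0.1324)/ln(0.85) = 0.87. Expected events are 200 × (0.15 + 0.1324) = 56.5, and Φ[√56.5 × (1 − 0.874)/(1 + 0.874) − 1.645] is about 13%. With a risk ratio of 1.5 or 3 it is about 9% or 18%.

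**5. Informative censoring.** Follow-up ends at attending takeover. If takeover tends to happen when a fall in saturation looks imminent, and its timing depends on the operator, the independence that protects the log-rank test in step 4 fails. The documents give nothing from which to size this.

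**The case against.** The strongest objection is that the primary analysis already deals with attempt length. It does, by censoring at success or takeover, and step 4 bears this out. A reader might infer from the 14–30% that the primary test has that error rate. The documents do not support this: those figures belong to the binary outcome, and the primary is affected only through the two further routes in steps 4 and 5.

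Other stronger readings also fail:

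- *Operator is not recorded at all.* The form was not available, and the induction-procedure category is broad enough to hold such a field. What can be said is that the protocol text names none.
- *The confounding could never be removed.* Section 29 (waiver of HIPAA authorization) says that only the outcome measurements are absent from the medical record, and that identifiers are kept so that incomplete data can be completed. Retrieval may be possible until the link is destroyed.
- *Section 11 lists who attempts the airway.* Its provider list concerns premedication only. Likewise "The sole difference will be nasal cannula placement after induction" describes procedure; it does not assert equal operators.
- *A child whose airway the attending starts cannot have the rescue outcome.* The outcome also counts temporary mask ventilation, so such a child remains evaluable. The documents do not describe attending-first cases.

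It is also fair to say that no shift is shown, that learner progression or rotation is not described, and that operator is only one of several factors that can vary by phase. What stands is that the design is open to such a shift and no planned analysis handles it.

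**Conclusion.** The point holds as a vulnerability, not as a demonstrated bias. Groups are non-concurrent, learner attempts are routine, and every planned comparison is unadjusted for operator. The analysis gap is there whatever the form contains; the recording gap is conditional on the form.

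For the binary secondary outcomes, a change in operator mix biases the contrast directly: about 14–30% false benefit instead of 5% under the assumed shares and risks, or power of 53–65% instead of 77% if the shift runs the other way. The time-to-95% comparison stays near 5% if operators differ only in attempt length. It is biased if operators differ in hazard at equal elapsed time, or if takeover is informative censoring. The real direction and size cannot be known from the documents. The change should be made, because it is cheap and retrieval is time-limited.

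**What to change.** 1. **Record** the first operator's level (attending, resident by training year, midlevel) on the data form if it is not already there. For completed forms, fill it in from the anesthesia record, where that names the operator, before the identity link is destroyed at study closure (sections 14, 25 and 29).
2. **Report** operator mix by phase.
3. **Binary secondary outcomes:** prespecify an analysis adjusted for or stratified by first-operator level, such as Mantel-Haenszel or logistic regression.
4. **Primary outcome:** prespecify a log-rank test stratified by first-operator level, or a Cox model including it.
5. **Composite of attending intervention or mask ventilation:** keep all children in it, report the two components separately, and also give the attending-intervention component among cases not started by the attending.

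Cost: one form field, a look-up for forms already collected, and one extra term or stratum in each analysis. No extra patients are needed. The downside is a slight loss of information if some operator strata have few events. Adjustment for operator also leaves other differences between the phases untouched.
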